**Table 2: Results of Largest Donor Lymphocyte Infusion Series for Myeloma**

Reference	N	Response Rate CR+PR	GVHD ≥2 (>Grade 2)	Comments
13	27	52% (22+30)	56% (15%)	Primarily T cell depleted transplant recipients
14	25	44% (28+16)	48% (24%)	Only 3 responders without GVHD
15	54	52% (17+35)	46% (20%)	T cell depleted patients primarily
16	11	90% (54+36)	50%	CD8 depleted DLI

Thus, in myeloma graft versus tumor responses seem to correlate with GVHD, possibly due to the fact that myeloma associated antigens that have been shown to be targets for the GVM effect are also

expressed in other tissues (17). Therefore, one possible strategy is to divert the GVM effect towards targets that are expressed primarily in myeloma cells and not in other tissues. This could increase the therapeutic efficacy of donor lymphocyte infusions. Vaccination with myeloma specific antigens is such an approach.

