## 6.0 Treatment Plan

### Idiotype Procurement

6.1 Recipient will undergo steady state plasmapheresis procedure to provide idiotype protein necessary to produce the vaccine. This is a standard procedure. Plasma (60-100 cc) from the plasmapheresis procedure will be sent to the MD Anderson Cancer Center GMP lab where it will be processed. The MDACC GMP lab will be responsible for producing the id-KLH conjugated vaccine according to the supplied standard operating procedure (see PDOL Appendices H and I). The vaccines will be kept in the GMP lab until requested. Alternatively vaccine can be produced using previously collected idiotype monoclonal protein collected on ongoing laboratory protocols and cryopreserved.

6.2 Donor will be vaccinated with an id-KLH vaccine 0.5 cc subcutaneously, once during weeks -8, -6, and -2 prior to donor lymphocyte collections.

The preferred site for the vaccine injection are the deltoid area (upper arm) and thigh. Sites should be alternated with each vaccine administration.

All donors will be observed in the clinic for two hours following vaccine administration. During the observation period, vital signs will be taken every 15 minutes during the first hour and then every 30 minutes during the second hour following vaccine administration.

6.3 GM-CSF 250 mcg/m^2 (dose rounded up to the nearest vial) S.C. will be given daily for four days (days 0-3) after each vaccine. All GM-CSF injections will be given in close proximity to the vaccination, as close to the exact site of injection as possible to ensure optimal recruitment of dendritic cells. The first dose of GM-CSF will be given by a nurse, and the remaining three doses will be given by the donor. Research staff will provide educational instructions regarding subcutaneous injection administration.

6.4 Recipient must meet the following criteria in order to receive the vaccine:

- Recipient to receive vaccine must be greater or equal than 3 months post allograft and with 5% or greater donor cell engraftment
- On a prednisone or prednisone equivalent dose of no more than 10 mg every other day at the time of registration, and with tacrolimus levels of <5 ng/dl or cyclosporine levels of < 100 ng/dl.
- Have no uncontrolled GVHD.

- Negative serum Beta HCG test in a woman with child bearing potential (not post-menopausal for 12 months or no previous surgical sterilization) and willing to use an effective contraceptive measure while on study.

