If the recipient does not meet the above "pre-vaccine" criteria, the recipient and donor will be taken off the study. The donor will have follow-up tests and procedures performed, as described in Section 7.0.

- 6.5 On day 0 (day of lymphocyte collection) donors will undergo a steady state pheresis to obtain lymphocytes. Donor target cell dose will be to  $\geq 2 \times 10^7$  CD3+ cells /kg recipient weight. If the target dose is not reached after 3 collections, then the donor and the recipient will be taken off the study and the apheresis product will be discarded.
  - 6.6 If successful collection, on day 0:  $1 \times 10^7$  CD3+/cells per kg will be infused into the recipient. The rest of the cells will be cryopreserved in  $5 \times 10^7$  CD3+ cells /kg recipient weight aliquot. Premedication will include only acetaminophen 650 mg po (orally) and benadryl 25 mg iv once.
- NO STEROIDS ARE TO BE GIVEN PRIOR TO LYMPHOCYTE INFUSION.
- 6.7 After DLI on same day, recipient will receive id-KLH vaccine. The vaccine will be also administered on week 4 and week 8 post DLI. The recipient will receive a total of 3 vaccines.
  - 6.8 For the donor the time of active treatment will begin the day of the first vaccine and finish 30 days after donor lymphocyte collection.
  - 6.9 For the recipient the time of active treatment will begin the day of the donor lymphocyte infusion and finish 30 days after the last vaccination.
  - 6.10 Recipients will receive GM-CSF 250 mcg/m^2 (rounded up to the nearest vial) S.C.daily for four days (days 0-3) after each vaccine. All GM-CSF injections will be given in close proximity to the vaccination, as close to the exact site of injection as possible to ensure optimal recruitment of dendritic cells. The first dose of GM-CSF will be given by a nurse, and the remaining three doses will be given by the recipient. Research staff will provide educational instructions regarding subcutaneous injection administration.
  - 6.11 Donors and/or recipients: Fever and chills associated with vaccine administration and/or GM-CSF will be treated with acetaminophen and/or meperidine. The use of non-steroidal anti-inflammatory drugs and/or steroids should be avoided.
  - 6.12 Recipients should not receive steroid premeds, or high dose steroids for other indications unless approved by the Study Chair or his designee.

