**B. Recipient:**

**Within 10 days prior to lymphocyte infusion and within 72 hours prior to each vaccine:**

- 1) H&P, vital signs.
- 2) Albumin, total protein, calcium, glucose, BUN, creatinine, bilirubin, ALT, alkaline phosphatase, LDH, CBC with differential, PT/PTT.
- 3) GVHD assessment.
- 4) Immunodeficiency panel.
- 5) Negative serum pregnancy test if of child bearing potential.
- 6) Disease specific assessment:
  - SPEP, UPEP, serum and immunofixation electrophoresis, serum for free kappa and lambda light chain assay, Beta 2 Microglobulin, and C reactive protein.

- 7) Collect 10 cc serum and 60 cc peripheral blood in preservative-free heparin for idiotype-specific antibody and cellular proliferative responses, immediately prior to donor lymphocyte infusion, 1 hour after the donor lymphocyte infusion.
- 8) Idiotype-specific humoral and cellular responses will be assessed in both donor and in the recipient post-transplantation.
- 9) Negative donor infectious disease panel:
  - Hepatitis B surface antigen (HBsAg)
  - Anti-Hepatitis B core antibody (HBcAb)
  - Anti-Hepatitis C Virus antibody (HCV Ab)
  - Anti-Human Immunodeficiency Virus (HIV) antibody (HIV 1/2 type O Ab)
  - Anti-Human T cell lymphotropic Virus (HTLV) antibody (HTLV I/II Ab)
  - Rapid Plasma Reagen (RPR)
  - Cytomegalovirus antibody (CMV)
  - HCV/HIV Nucleic Acid Test
  - West Nile Virus Nucleic Acid Test
  - Sickledex
  - T Cruzi AB

Additional tests shall be performed as required to assess the possibility of transmission of other infectious or non-infectious diseases.

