## **9.0 Criteria for Removal from the Study**

1. Patient/Donor withdrawal of informed consent
2. Patient death
3. Disease progression requiring anti-myeloma therapy
4. Patient/ Donor not being compliant
5. 5 years post donor lymphocyte infusion
6. If the recipient does not meet the "pre-vaccine" criteria in Section 7.0 B., the recipient and donor will be taken off the study.
7. Donor lymphocyte collection failure
8. An increasing or unexpected pattern of toxicity observed deemed unacceptable by the study chairman
9. Investigator judgment when the well being and best interest of the patient is compromised.
10. Inability of donor to provide lymphocytes after study registration

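### The plan does not agree with itself on when the pre-vaccine criteria apply; read literally, it drops recipients with uncontrolled GVHD after DLI and loses their later response, GVHD and immune data

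*Combined protocol and SAP*

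**What the plan says.** Section 6.4 opens with "Recipient must meet the following criteria in order to receive the vaccine". Its list includes "Have no uncontrolled GVHD", with no definition of uncontrolled and no time point on that item. The steroid item does carry one: "On a prednisone or prednisone equivalent dose of no more than 10 mg every other day at the time of registration". For a recipient who does not meet the pre-vaccine conditions, the next paragraph reads "criteria, the recipient and donor will be taken off the study. The donor will have follow-up tests and procedures performed". It describes no further follow-up for the recipient.

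Under Section 6.7 the first recipient vaccine is given after DLI on the same day, and then "The vaccine will be also administered on week 4 and week 8 post DLI".

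Section 9.0 item 6 repeats the removal but locates the conditions elsewhere: "criteria in Section 7.0 B., the recipient and donor will be taken off the study". Section 7.0 B is a list of assessments, GVHD among them, timed "Within 10 days prior to lymphocyte infusion and within 72 hours prior to each vaccine". It sets no GVHD threshold.

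Section 8.0 names anti-myeloma response and GVHD as the primary clinical endpoints and allows GVHD to be treated, without mentioning removal. Section 10.0 models CTL counts out to week 12, counts toxicity over 6 months after DLI and caps the trial at 10 patients. It does not say how a recipient taken off study is analysed.

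**The concern.** The criteria govern receipt of a vaccine that recipients get only after DLI, and item 6 ties removal to checks repeated before each vaccine. A site applying those two texts as written would take a recipient who already has the vaccinated-donor cells off study at week 4 or 8 because GVHD had developed. GVHD is a named endpoint and an expected effect of DLI.

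The background section says responses to DLI appear to go together with GVHD, and Table 2 notes of one 25-patient series "Only 3 responders without GVHD". Leaving the study because of GVHD would therefore be related to response. The PR/CR rate (objective 2.1), the later GVHD rate (objective 2.2) and the tail of the CTL curve would then describe recipients selected partly on an outcome. With at most 10 recipients, each one is a tenth of the sample, and assessments not made after removal cannot be recovered at analysis.

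**Working it through.** The plan attaches no figure to this rule. Its only recomputable design figures are the stopping probabilities in the toxicity table. The stated posterior rule gives .340, .516, .708 and .877 against the printed .35, .52, .70 and .88, and they are not in dispute here.

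**When do the criteria apply?**

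- For a single check before DLI: Section 6.4 stands before collection (6.5) and infusion (6.6); it asks for at least 3 months since allograft and a minimum engraftment; and the steroid limit is fixed at registration.
- For a check before every vaccine: Section 6.4 is worded as a condition for receiving the vaccine, all three recipient vaccines follow DLI, the GVHD item is undated, and item 6 points to Section 7.0 B, which is repeated before each vaccine.

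No text settles the matter.

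**What a recipient removed at week 4 or 8 would have, and lose**

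- Already collected: idiotype samples immediately before and 1 hour after DLI, and M-protein tests before that vaccine. The month 1 and 2 samples in Section 7.0 D may fall on either side of removal.
- Lost: the week 12 CTL value, and also week 8 if removed at week 4; all 3, 6, 12, 18 and 24 month visits with marrow restaging, GVHD and idiotype assessment; and scheduled observation for the rest of the 6-month GVHD window. Taking 6 months as 26 weeks, that is 26 − 4 = 22 or 26 − 8 = 18 weeks.

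**How many recipients**

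Let u be the share with uncontrolled GVHD at a week 4 or week 8 check. The documents give no such rate, so u is an assumption. The top value, 24%, is the largest share above grade 2 in Table 2. Expected number lost = 10u; P(at least one) = 1 − (1 − u)^10. For example, at u = 5%: 1 − 0.95^10 = 1 − 0.599 = 0.401.

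| u | Expected lost of 10 | P(at least one) |
|---|---|---|
| 5% | 0.5 | 40% |
| 10% | 1.0 | 65% |
| 15% | 1.5 | 80% |
| 20% | 2.0 | 89% |
| 24% | 2.4 | 94% |

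**Direction of the effect on response (illustration only)**

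In the 25-patient series in Table 2, responders = 25 × 0.44 = 11, of whom 3 had no GVHD and 8 did. GVHD of grade 2 or more = 25 × 0.48 = 12. If the comment refers to that group, response was 8/12 = 67% with GVHD and 3/13 = 23% without. Assume that those removed respond at the 8/12 rate:

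- Remove 3 (12%): 3 × 8/12 = 2 responders lost. The rate goes from 44% to 9/22 = 41% if they are excluded, or 9/25 = 36% if they count as non-responders.
- Remove 6 (24%): 4 responders lost. The rate becomes 7/19 = 37%, or 7/25 = 28%.

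Grade here stands in for uncontrolled GVHD, which is a different and undefined event. The figures show direction and rough scale; they do not estimate the bias in this trial.

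**The case against.** The best reply is that the rule is an entry gate. Section 6.4 precedes DLI, its contents look like registration conditions, and donor-only follow-up makes sense if the donor has been vaccinated and the recipient has had no study treatment. Item 6 may simply carry a wrong cross-reference, since Section 7.0 B sets no threshold. Section 8.0 expects GVHD to be treated on study, and Section 6.13 withholds later infusions when GVHD is active, which presumes that some recipients with GVHD remain. These arguments have weight: a reader might infer that the plan expressly re-applies the criteria at weeks 4 and 8, and it does not. But the entry-gate reading is not stated either, and it leaves item 6 pointing at a section done before each vaccine. The texts still need reconciling.

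A reader might also infer that response and immune transfer would go entirely unassessed. The early samples and M-protein tests rule that out. The adverse event section follows an ongoing event after removal unless another therapy is started, and serious events are followed to recovery or stabilisation. A qualifying grade 2-4 event would usually be known before removal, so the toxicity count is less exposed. None of this supplies later restaging, chronic GVHD or idiotype data.

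Finally, it is tempting to say that the rule removes those with the strongest donor effect. The documents do not support that for the primary aim: vaccination is meant to direct the effect away from targets shared with other tissues, so GVHD severity does not measure idiotype-specific transfer.

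**Conclusion.** Sections 6.4, 7.0 B and 9.0 item 6 do not agree on when the pre-vaccine criteria apply. Under a literal reading of 9.0 with 7.0 B, recipients with uncontrolled GVHD after DLI leave the study, and their later data are lost in a way related to response. The expected loss is 0.5 to 2.4 of 10 recipients, with a 40% to 94% chance of at least one. This rests on an assumed 5% to 24% for the trigger, independence between recipients, 10 recipients treated, and a site taking the literal reading. A reader could apply the Table 2 rates for grade 2 or higher GVHD directly and conclude that up to about 5 of 10 would go. That does not follow, because controlled GVHD of those grades does not trigger removal and not all of it would begin by week 8.

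The point is worth correcting but does not undermine the trial. This is a feasibility study, and no decision threshold rests on the PR/CR rate.

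**What to change.** Reconcile Section 6.4, the paragraph after it, Section 7.0 B and Section 9.0 item 6 so that they state one time, or set of times, at which the criteria apply, and make item 6 refer to the section that contains them. Confine off-study removal under this rule to recipients who have not received DLI. State that any recipient given DLI stays on the existing Section 7.0 B and 7.0 D disease, GVHD and idiotype schedule whether or not later vaccines are given, and stays in the PR/CR and GVHD denominators. In Section 10.0, say that GVHD treatment will be flagged in the CTL analysis. Whether a later vaccine is given is for the sponsor to decide; the change only separates not receiving a vaccine from leaving the study.

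The cost is one wording amendment and a few recipients completing visits and blood draws already in the schedule. Their CTL curves will include the effect of GVHD treatment, which the flag makes visible but does not remove.

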## Protocol Body

### 1.0 Objectives

1. Primary
  - 1.1 Determine whether transfer of myeloma specific immunity is enhanced by vaccinating donors prior to donor lymphocyte infusion with an id-specific vaccine.
2. Secondary
  - 2.1 To determine the rate of partial response (PR) and complete response (CR) in patients receiving donor lymphocytes (recipients) from an id-specific vaccinated donor.
  - 2.2 To determine the GVHD rates after donor lymphocyte infusion from an id-specific vaccinated donor.

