Similar clinical results were observed in multiple myeloma patients. At the University of Turin 12 patients with myeloma received high-dose chemotherapy and autologous stem cell transplantation followed by vaccination with Id-specific proteins conjugated to KLH and GM-CSF or IL-2 as immunoadjuvants (30). Id-specific T cell proliferative responses were documented in 2 patients, and a positive Id-specific delayed-type hypersensitivity reaction was observed in 8 of the 10 patients studied. Twelve patients with multiple myeloma were treated at Stanford University with high-dose therapy and peripheral blood stem cell transplantation followed by Id immunizations (31). Following transplantation patients received a series of monthly immunizations consisting of Id-pulsed autologous dendritic cells followed by subcutaneous (S.C.) boosts of Id conjugated to KLH. The administration of Id-pulsed DC and Id-KLH vaccines was well tolerated with patients experiencing only minor and transient side effects. Two of 12 patients developed an Id-specific, cellular proliferative immune response, and one of three patients studied developed a transient but Id-specific cytotoxic T cell response. Similarly, investigators at the University of Wales were able to generate dendritic cells from six patients with IgG myeloma, and the cells were pulsed with the

autologous Id (32). Id-specific responses were also observed. PBMC proliferative responses to Id were observed in five of the six patients following treatment. These initial trials demonstrate that the vaccination of patients was relatively safe and capable of producing Id-specific T cell responses.

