## **10.0 Statistical Considerations**

**Preliminaries.** This is a single-arm feasibility trial of Id Specific vaccinated DLI for treatment of multiple myeloma patients post allograft from a matched sibling donor who are not in CR or relapsing after transplant at least 3 months after stem cell transplant. The last myeloma therapy must be at least 3 weeks prior to entry. Labeling time of DLI as week 0, each donor will be vaccinated at weeks -8, -6, -2 and each patient will be vaccinated at weeks, 0, 4, and 8. Toxicity (TOX) will be defined as the event that the patient suffers grade 2, 3 or 4 GVHD or death within 6 months post DLI. The historical rate of TOX is 50% (54/107). The primary aim is to determine whether transfer of myeloma specific immunity is enhanced by vaccinating donors prior to donor lymphocyte infusion with an id-specific vaccine.

**Trial Conduct.** A maximum of 10 patients will be treated.

**Analysis of Myeloma Specific CTLs over time.** A generalized linear mixed model (Diggle, et al., 1998) will be fit to the longitudinal measurements of myeloma specific CTLs. For patient  $j = 1, \dots, 20$  at observation time  $t = -8, -6, -2, 0, 4, 8, 12$ , denote the myeloma specific CTL count by  $Y_{j,t}$  and covariate vector by  $Z_j$ . The model is given by

$$g\{E(Y_{j,t})\} = m + f_j(t) + b Z_j + \text{error}$$

where  $g$  is a suitable link function,  $m$  is the overall mean,  $f_j$  is a patient-specific function of  $t =$  time from day of DLI, accounting for the manner in which  $Y$  varies over time and includes a patient effect to account for correlation among the successive observations on each patient,  $Z_j$  is a component accounting for patient covariates with  $b$  is a covariate parameter vector, and "error" is the usual measurement of error.

Additional analyses of the final data will include analysis of survival times as functions of the treatments and patient prognostic covariates using an appropriate survival regression model determined by goodness-of-fit analyses.

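### The planned CTL model cannot credit a rise after DLI to donor vaccination: recipients are vaccinated too, and no donor goes unvaccinated

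*Combined protocol and SAP*

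**What the plan says.** Section 1.0 gives the primary objective: "Determine whether transfer of myeloma specific immunity is enhanced by vaccinating donors prior to donor lymphocyte infusion with an id-specific vaccine". Section 10.0 repeats it ("The primary aim is to determine whether transfer of myeloma specific immunity is enhanced by vaccinating donors prior to donor lymphocyte infusion") and describes the design: "This is a single-arm feasibility trial of Id Specific vaccinated DLI", with at most 10 patients.

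Donors are vaccinated at weeks -8, -6 and -2. For recipients, section 6.7 says "After DLI on same day, recipient will receive id-KLH vaccine", and section 10.0 agrees: "each patient will be vaccinated at weeks, 0, 4, and 8". Under section 3-A both members of the pair get the same patient-specific Id-KLH product with GM-CSF.

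The CTL analysis in section 10.0 is a generalized linear mixed model at weeks -8, -6, -2, 0, 4, 8 and 12. Its terms are an overall mean, a patient-specific function of time, patient covariates and error. Nothing in it represents donor or recipient vaccination.

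Section 7.0 B, item 7 schedules recipient blood "immediately prior to donor lymphocyte infusion, 1 hour after the donor lymphocyte infusion", for antibody and proliferative responses. It does not place the 1-hour draw before or after the same-day vaccine.

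**The concern.** Both statements of the aim name donor vaccination alone. The only measurements that could show immunity in the recipient after transfer are taken once the recipient has been vaccinated with the same antigen. A rise over weeks 4 to 12 could come from transferred donor cells, from the recipient's own response, or from DLI as it would act with an unvaccinated donor. The planned model treats all three alike.

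The Background proposes this trial because donor immunization was hard to evaluate alongside a primary allograft. Moving to the DLI setting removes that confounder, but the planned analysis introduces two others. At stake is whether the trial's main conclusion can be stated in the words of its primary aim.

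**Working it through.** The plan gives no power, alpha or effect size for the CTL aim, so there is no figure to reproduce. The check is a dose count followed by an estimability check.

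**Inputs**
- Donor vaccine weeks -8, -6, -2 (sections 6.2 and 10.0); recipient vaccine weeks 0, 4, 8 (sections 6.7 and 10.0).
- Modelled weeks -8, -6, -2, 0, 4, 8, 12 (section 10.0).
- Donor immune bloods stop at week 0 (section 7.0 A). Recipient bloods are drawn around DLI and at months 1, 2, 3 and later (section 7.0 B and D). I therefore read weeks 4, 8 and 12 as recipient measurements.

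**Step 1: recipient doses before each modelled time**, taking each blood as drawn before that visit's vaccine, and week 0 as before DLI:

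| Week | Donor doses so far | DLI given | Recipient doses so far |
|---|---|---|---|
| -8 | 0 | no | 0 |
| -6 | 1 | no | 0 |
| -2 | 2 | no | 0 |
| 0 | 3 | no | 0 |
| 4 | 3 | yes | 1 |
| 8 | 3 | yes | 2 |
| 12 | 3 | yes | 3 |

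If blood at weeks 4 and 8 were drawn after that visit's vaccine, the last three counts would be 2, 3, 3. Either way, 3 of 3 modelled times after DLI follow recipient vaccination.

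**Step 2: what the recipient data can estimate.** Use the columns (intercept, DLI received, donor vaccinated, recipient vaccinated). Every patient contributes the same rows:
- week 0: (1, 0, 0, 0)
- weeks 4, 8, 12: (1, 1, 1, 1)

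There are two distinct rows, so the rank is 2 of 4. The donor effect is the contrast (0, 0, 1, 0), which is not a combination of these rows, so it is not estimable. More patients would only repeat the rows.

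A finer coding does not help. All pairs share one schedule, so any coding of recipient vaccination, including the count 1, 2, 3, is a function of week alone, and the model's free function of time absorbs it. The DLI and donor columns stay identical.

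**Step 3: add a 1-hour sample drawn before the recipient's first dose.** The new row is (1, 1, 1, 0) and the rank becomes 3 of 4. Recipient vaccination now separates from the infusion: (1, 1, 1, 1) - (1, 1, 1, 0) = (0, 0, 0, 1). DLI and donor vaccination still share a column, so the donor effect remains inestimable.

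**Step 4: add unvaccinated-donor pairs on the same recipient schedule to the planned times.** The new row after DLI is (1, 1, 0, 1), and (1, 1, 1, 1) - (1, 1, 0, 1) = (0, 0, 1, 0). The donor effect becomes estimable.

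The plan has no such comparator. The historical rate in section 10.0 concerns toxicity, and the DLI series in Table 2 report clinical response and GVHD, not CTL counts.

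**The case against.** The strongest defence is that this is a feasibility trial in at most 10 patients, with no test, alpha or success threshold for CTLs. The Background also cites preclinical work on combined donor and recipient immunization, so the combined regimen may be deliberate. That is fair, and it means nobody can say the investigators would report a rise as enhanced transfer. It does not reconcile the aim with the analysis: both statements of the aim name donor vaccination only, and section 10.0 specifies a model in its support.

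Three stronger readings are tempting but unsupported.

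- *Recipient vaccination is the whole problem, so the 1-hour sample cures it.* Step 3 shows otherwise. Without any recipient vaccination, donor vaccination would still be confounded with DLI. The 1-hour draw is also listed for antibody and proliferative assays, not CTLs, and its order relative to the vaccine is unstated.
- *The Background gives the size of the false signal.* It reports "Two of 12 patients developed an Id-specific, cellular proliferative immune response" and "PBMC proliferative responses to Id were observed in five of the six patients following treatment". The first series used Id-pulsed dendritic cells followed by Id-KLH boosts, the second Id-pulsed dendritic cells. Neither is the product used here, and both counts are of proliferation, not CTLs. They make a recipient response of its own plausible but do not measure it.
- *Adjusting for the donor's week-0 level rescues weeks 4 to 12.* The recipient's vaccine schedule is constant across pairs, but the recipient's response to it need not be. Recipients already carry donor cells from the allograft (section 6.4 asks for at least 5% engraftment). If the same donor is used, a donor who responds well could be paired with a recipient who responds well without any new transfer.

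**Conclusion.** The concern holds in this form: the planned CTL model cannot attribute a rise at weeks 4 to 12 to donor vaccination, for two reasons. Every modelled time after DLI follows recipient vaccination (3 of 3), and every donor in the single arm is vaccinated, which ties donor vaccination to DLI itself (rank 2 of 4; donor effect not estimable).

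This rests on the stated schedules, on weeks 4, 8 and 12 being recipient measurements, and on the absence of a comparator. It does not depend on sample size or any assumed response rate. The documents do not allow the size of any misattribution to be estimated, and none is claimed. Donor samples up to week 0 can still show that donors were immunised, and weeks 4 to 12 can still describe the combined regimen.

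**What to change.** Change the statistical section, and the wording of the aim where needed. Treatment stays as it is.

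1. State that weeks 4 to 12 estimate the combined effect of DLI from a vaccinated donor plus recipient vaccination. Restate the primary aim or conclusion to match, and note that enhancement by donor vaccination is not estimable without an unvaccinated-donor comparator.
2. Name two separate supportive contrasts: the donor's change from week -8 (before vaccine) to week 0, for immunisation; and the recipient's change from immediately before DLI to 1 hour after, for early transfer. Enter before and after DLI as two model times instead of one t = 0. Record whether the 1-hour draw preceded the same-day vaccine, and state which assay is used.
3. Label any association between the donor's week-0 level and recipient levels at weeks 4 to 12 as exploratory.

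The cost is mostly wording, since these bloods are already scheduled. CTL assays on the bloods before DLI and at 1 hour may add some laboratory work. The primary claim becomes narrower, and the 1-hour contrast shows only early passive transfer, not persistence, expansion or enhancement.
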